8.3.6. Disease-Related Events and/or Disease-Related Outcomes Not Qualifying as AEs

The following disease related events are common in participants with AD:

- AD
- Eczema
- Flare of AD

Because these events are expected in this remitting and relapsing disease, they will not be reported as AEs. These events should be documented and recorded on the appropriate CRF as occurrence of a flare of AD during the maintenance period represents the efficacy outcome measure.

NOTE: However, if either of the following conditions applies, then the event must be recorded and reported as an AE:

- In the investigator's opinion, the event is of greater intensity or severity than the individual participant's condition at baseline (Day 1 of the run-in period).

OR

- The investigator considers that there is a reasonable possibility that the event was related to study intervention.

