9.4.1.2. Analysis Methods

Endpoint	Statistical Analysis Methods
Primary	
Primary Analysis
 
Time of flare-free maintenance in the first QD period up until the onset of the first flare during the 52-week maintenance period will be analyzed using a log-rank test, stratified by age group, duration of the BID treatment in open-label period, and ISGA score (clear [0], almost clear [1]) at randomization to test the difference between crisaborole QD versus vehicle QD. The proportion of participants maintaining flare-free at each month until the first flare onset in the maintenance period will be estimated by the product limit method; the median time of flare-free up until the first flare onset will also be estimated by this method. This analysis will be based on Estimand 1 using the Evaluable-DB population (see Section 9.1 and Section 9.3 for estimands and populations).
 
Sensitivity/Supplementary Analysis
 
For the above primary analysis, the flare is based on the investigator assessment of ISGA; time of flare is ISGA assessment time. Before investigator assessment, the flare may already have occurred. As a sensitivity analysis, flare is defined as participants reported AD worsening event. Analysis method and intercurrent events handling are the same as above for the primary analysis.
 
Another sensitivity analysis is interval censoring survival analysis. Time of flare is between the time of participants reported AD worsening and the time of investigator confirmed ISGA ≥ 2. This analysis will be based on Estimand 1 using the Evaluable-DB population.

Secondary	
Number of flare-free days will be analyzed using an analysis of covariance model, with treatment, age, duration of the BID treatment in open-label period, and ISGA score (clear [0], almost clear [1]) at randomization as factors. The number of flare-free days is total duration across the double-blind QD periods in the study for each participant. This analysis will be based on Estimand 2 using the Evaluable-DB population.

Endpoint	Statistical Analysis Methods

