2.1.1. Estimand 1 for the Primary Endpoint

Estimand 1: The primary estimand of the main study is a hypothetical estimand, defined according to the primary objective and is in alignment with the primary endpoint. It includes the following 4 attributes:

- Population: Patients who are treated with crisaborole 2% BID up to 8 weeks and achieve response defined by the criteria in the protocol.
- Variable: Duration of flare-free maintenance up until the onset of the first flare during the DB period.
- Intercurrent events: intercurrent events include discontinuation of treatment. If an event (eg, death, dropout, loss to follow up, or end of study) occurs before the first flare, the duration of flare-free maintenance is the time from randomization to the first intercurrent event and is censored. When a flare occurs first, the duration of flare-free maintenance is the time from randomization to the first flare and is not censored.
- Population-level summary: Median duration of flare-free maintenance during the DB period, proportion of participants who are flare-free by time point in each treatment group.

This estimand framework will be used for other time-to-event endpoints as well, such as maintenance of EASI response at randomization, maintenance of dermatology quality of life and maintenance of POEM.

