6.1.1. Main Analysis

- Estimand strategy: Hypothetical ([Section 2.1.1](#)).
- Analysis Population: Evaluable-DB.
- Analysis method: Time-to-event analysis, Kaplan-Meier (product limit) method and log-rank test ([Section 5.2.4](#)).
- Intercurrent events: intercurrent events include discontinuation of treatment. If an intercurrent event (eg, death, dropout, loss to follow up, or end of study) occurs before the first flare, the duration of flare-free maintenance is the time from randomization to the first intercurrent event and is right censored. When a flare occurs first, the duration of flare-free maintenance is the time from randomization to the first flare and is not censored.

- Reporting results: At each month, the proportion of participants who had maintained flare-free status before the first flare, time-to-event curve, median (95% CI) time of maintaining flare-free, and number (%) of censored participants for each treatment group, and p-value from log-rank test will be presented.

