6.1.2. Sensitivity/Supplementary Analysis

For the above main analysis, the definition of flare is based on the investigator assessment of ISGA, time of flare is the assessment time when ISGA \geq 2. In addition, a sensitivity analysis will be performed where flare definition includes an AD worsening event (preferred term= Dermatitis atopic or Eczema) reported by a participant prior to a confirmatory ISGA \geq 2. In this analysis, the time of onset of such event will be used as the onset of the flare. If a participant reported an AD worsening event but the investigator assessment is not a flare at the subsequent visit, this event is not a flare. Estimand strategy, analysis population, analysis method and intercurrent events handling are the same as above for the main analysis.

Another sensitivity analysis is interval censoring survival analysis. Time of flare is between the time of participants reported AD worsening and the time of investigator confirmed ISGA \geq 2. Because the exact flare time is not known, the midpoint of the above interval will be used as the flare time. Estimand strategy, analysis population, analysis method and intercurrent events handling are the same as above for the main analysis.

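### The interval-censoring sensitivity analysis in SAP 6.1.2 is a midpoint imputation, and it hardly tests the flare-dating uncertainty left by 56-day gaps between scheduled ISGA visits

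*SAP*

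**What the plan says.** Protocol 9.4.1.2 gives two sensitivity analyses of the primary endpoint, because a flare may have begun before the investigator saw it. On the second it says "Another sensitivity analysis is interval censoring survival analysis", and "Time of flare is between the time of participants reported AD worsening and the time of investigator confirmed ISGA" of 2 or more. It has no midpoint rule.

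SAP 6.1.2 keeps the label and the interval and adds "Because the exact flare time is not known, the midpoint of the above interval will be used as the flare time". Population, method and handling of intercurrent events are those of the main analysis, which is Kaplan-Meier with a stratified log-rank test on right-censored times (SAP 5.2.4, 6.1.1). The main analysis dates a flare at the ISGA assessment.

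The figures that depend on flare dates are part of the estimand. SAP 2.1.1 gives the population-level summary as "Median duration of flare-free maintenance during the DB period, proportion of participants who are flare-free by time point in each treatment group", and the first item that SAP 6.1.1 reports is "At each month, the proportion of participants who had maintained flare-free status before the first flare".

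In the Schedule of Activities, ISGA is scored at in-clinic visits, and Weeks 20, 28, 36 and 44 are phone visits. Protocol 4.1 asks participants to contact the site promptly if they suspect a flare, and Protocol 8 has the phone visits ask about suspected flares.

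**The concern.** An interval-censored analysis keeps the interval for each event and lets the likelihood reflect it. Putting one date in the middle and running Kaplan-Meier treats that date as observed.

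The interval itself is also the narrow one. It runs from report to clinic visit, so it covers the delay in getting an appointment. It does not cover the time since the skin was last seen to be clear or almost clear. A flare first noticed at a scheduled visit has no report and therefore no left end. The first sensitivity analysis adds reported worsening to the flare definition, which implies that other flares keep the ISGA date. The second states no such rule. These unreported flares have the least certain dates.

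At stake is whether the plan contains any check of the median and the monthly flare-free proportions against visit spacing.

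**Working it through.** **1. The plan's own figure.** Protocol 9.2 gives 162 events, HR 0.556, two-sided 0.05 and 1:1 allocation. Schoenfeld: z = √162 × |ln 0.556| / 2 − 1.96 = 12.73 × 0.587 / 2 − 1.96 = 1.78, so power is 96.2%. The stated 96% reproduces.

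**2. Visit gaps.** Scheduled ISGA falls at Weeks 4, 8, 12, 16, 24, 32, 40, 48 and 52. Gaps are 28 days to Week 16, (24 − 16) × 7 = 56 days from Week 16 to Week 48, then 28 days.

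**3. Flare rate (derived, not planned).** With exponential onset, no dropout and 162/250 = 0.648 flaring in 364 days, solve ½(1 − e^(−364λ)) + ½(1 − e^(−364 × 0.556λ)) = 0.648. This gives λ = 0.003856 per day on vehicle. True medians are ln 2/λ = 180 days and 180/0.556 = 323 days.

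**4. Error at Week 20 (Day 140), by hand.** Assume that flares persist until detected, that a share p is reported at onset, and that ISGA follows a report by 7 days on average. Unreported flares since Week 16 are still unseen: S(112) − S(140) = 0.6493 − 0.5828 = 6.65 points. A flare first mentioned in the Week 20 call is confirmed only after it, so the call does not help at Week 20. Reported flares awaiting ISGA are about λ × S(140) × 7 = 0.003856 × 0.5828 × 7 = 1.57 points. The main error is 6.65(1 − p) + 1.57p. The midpoint halves only the second term.

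| Share reported | Main, points too high | Midpoint, points too high |
|---|---|---|
| 25% | 5.38 | 5.18 |
| 50% | 4.11 | 3.72 |
| 75% | 2.84 | 2.25 |
| 90% | 2.08 | 1.37 |
| 100% | 1.57 | 0.79 |

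**5. Simulation over a range of assumptions.** Dropout 0-20%; 0-100% of unreported flares caught by phone; mean lag 3.5 or 7 days; flares persist until detected. Vehicle arm, Weeks 20, 28, 36 and 44, points too high:

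| Share reported | Main | Midpoint | Dating error removed by midpoint |
|---|---|---|---|
| 25-75% | 1.1-5.9 | 0.9-5.8 | 2-26% |
| 90% | 0.5-2.4 | 0.3-1.7 | 28-38% |
| 100% | 0.3-1.8 | 0.1-1.0 | 50% |

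Crisaborole at 25-75% reporting: main 1.0-4.2, midpoint 0.9-4.0. At the nine four-weekly points with a scheduled ISGA, the main analysis is within 0.3 points if visits take place in clinic. If 10% of them are missed, as the phone contacts of Protocol Appendix 9 could cause, the error there is 0.0-1.1 in the central case (no dropout, half of unreported flares caught by phone, 7-day lag).

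Vehicle median in the central case (true 180 days), main / midpoint / interval-censored at scheduled visits: 197/195/180 at 50% reporting and 187/184/180 at 90%.

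**6. The test.** In simulated trials of 125 per arm, the midpoint changed the log-rank Z by 0.01-0.04 on average, against a mean Z of −3.4 to −4.0.

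**7. Choice of right end.** If the interval ends at the flare-triggered visit, the nonparametric estimate is 2.8-6.7 points too low at the four weeks, and the vehicle median is 169 days against 180. The flare itself prompts that visit, so its date carries information about onset. Grouping to scheduled visits avoids this and left power almost unchanged (94.8-96.7% against 94.7-96.9%) when both arms report equally.

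**The case against.** This is a sensitivity analysis with no alpha and no place in the testing order. Its stated purpose is the delay between report and ISGA, which a midpoint does address. The protocol also encourages reporting, and at 90-100% the main error is at most 2.4 points. All of that stands. It is why the midpoint should stay under a correct name, and why visit spacing is a question to add beside it.

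A reader might infer that a true interval-censored analysis recovers the right curve whatever share is reported. The simulation shows that only if an undetected flare lasts until the next ISGA, and the documents do not support this as a general assumption. Protocol 2.2 cites flares of about 14 days, and Protocol 4.2 cites a median of 84 days to regain clear or almost clear skin. In central-case runs where unreported flares could resolve, the interval-censored vehicle estimate at the four weeks was also too high. With a median of 84 days, the excess was 1.3-4.3 points at 25-75% reporting and 0.7-0.8 at 90%. With a mean of 14 days, it was 10.7-14.3 points at 50% and 2.6-2.9 at 90%. It was still less biased than the midpoint in every case run.

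Grouping to scheduled visits also has a price. A flare confirmed on Day 120 would get the interval from Day 113 to Day 169, and that later visit may never take place because the participant has moved to flare treatment.

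A reader might also infer that the first sensitivity analysis has no data. It uses "flare definition includes an AD worsening event (preferred term= Dermatitis atopic or Eczema) reported by a participant prior to a confirmatory" ISGA of 2 or more, while Protocol 8.3.6 says of AD, eczema and flare "Because these events are expected in this remitting and relapsing disease, they will not be reported as AEs". But the same section continues "These events should be documented and recorded on the appropriate CRF as occurrence of a flare of AD during the maintenance period" and lists exceptions that do go on the AE page. Whether that form is dated or coded cannot be judged without the CRFs, so the documents do not support the inference.

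**Conclusion.** The concern holds for labelling, completeness and reach. SAP 6.1.2 does not deliver the interval-censored analysis that the protocol names. It gives no rule for unreported flares, and it hardly tests visit-spacing uncertainty unless most flares are reported.

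A reader might take this as a threat to the primary result. It is not: the log-rank conclusion and the 96% power stand. The effect is on the median and the flare-free proportions, chiefly at the four phone-visit weeks. There the main analysis of the vehicle arm is about 1-6 points too high at 25-75% reporting and 0.3-2.4 at 90-100%. These sizes rest on exponential onset, the derived flare rates, assumed reporting shares and flares that persist until detected. The defect in the text rests on none of them. The change should be made before database lock, but the primary analysis does not depend on it.

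**What to change.** - In SAP 6.1.2, call the existing analysis midpoint imputation and state that a flare without a prior report keeps its ISGA date.
- Add an interval-censored analysis: nonparametric maximum likelihood for the curves and a generalised log-rank test with the SAP 5.2.4 strata. The left end is the last ISGA actually assessed at 0-1. Participants without a detected flare are right-censored at their last ISGA of 0-1.
- Report it with the right end grouped to the scheduled ISGA visit at or next due after detection. Report it also with the right end at the first ISGA of 2 or more, labelled as an early limit because flare-triggered visits make it too low.
- The estimator does not fix the curve inside a gap, so give Weeks 20, 28, 36 and 44 as a range between adjacent scheduled visits or by stated linear interpolation.
- State that the estimate assumes undetected flares persist to the next ISGA, and that it is too high if they resolve.
- Align the sentence in Protocol 9.4.1.2.

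Cost: SAP text, one protocol sentence and some extra programming, mostly on ISGA dates already collected. The grouped version coarsens unscheduled-visit dates and may need nominal dates where the next visit was not held.

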6.2. Key Secondary Endpoints

6.2.1. Number of Flare-Free Days

The first key secondary endpoint is the number of flare-free days during the DB period. It is the total flare-free days during the DB period for each participant regardless censoring or not, ie, the censored number of flare-free days in a flare-free period is truncated at censoring for the calculation of total number of flare-free days.

- Estimand strategy: Hypothetical ([Section 2.1.2.1](#)).
- Analysis Population: Evaluable-DB.
- Analysis method: ANCOVA model ([Section 5.2.2.2](#)).
- Intercurrent events: intercurrent events include discontinuation of treatment. Addressing intercurrent events for the duration of flare-free maintenance at each flare-free period is the same as that for the primary endpoint during the first flare-free period.
- Reporting results: The LS mean along with the corresponding standard error and 95% CI for each treatment group, LS mean difference along with the corresponding p-value, standard error and 95% CI will be presented.

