2.1.2. Estimands for Secondary Endpoints

2.1.2.1. Estimand 2

Estimand 2: The second estimand of the study for the secondary endpoint of number of flare-free days during the DB period is a hypothetical estimand. It includes the following 4 attributes:

- Population: Patients who are treated with crisaborole 2% BID up to 8 weeks and achieve response defined by the criteria in the protocol.
- Variable: Flare-free days during the DB period. It is the total days that the participant has no flare during the DB period for each participant.
- Intercurrent events: intercurrent events include discontinuation of treatment. Addressing intercurrent events for the duration of flare-free maintenance at each flare-free period is the same as that for the primary endpoint during the first flare-free period.
- Population-level summary: Difference in least-square means between crisaborole ointment, 2%, QD and vehicle QD for flare-free days over 52 weeks.

2.1.2.2. Estimand 3

Estimand 3: The third estimand of the study for the secondary endpoint of number of flares during the DB period is a hypothetical estimand. It includes the following 4 attributes:

- Population: Patients who are treated with crisaborole 2% BID up to 8 weeks and achieve response defined by the criteria in the protocol.
- Variable: number of flares during the DB period.
- Intercurrent events: intercurrent events include discontinuation of treatment.
- Population-level summary: Median difference between crisaborole ointment, 2%, QD and vehicle QD for number of flares over 52 weeks.

2.1.2.3. Estimand 4

Estimand 4: The fourth estimand of the study for the secondary endpoint of maintenance of pruritus response up until the onset of the first flare (ISGA ≥ 2) is a hypothetical estimand. It includes the following 4 attributes:

- Population: Patients who are treated with crisaborole 2% BID up to 8 weeks and achieved pruritus response defined as ≥ 2 , 3, or 4 points of improvement from OL baseline in respective pruritus scales (See Section 3.2.1).
- Variable: Duration of maintenance of pruritus response up until the onset of the first flare (ISGA ≥ 2).

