5.2.2.2. Non-longitudinal Continuous Data

Analysis of covariance (ANCOVA) will be used to analyze non-longitudinal continuous data, such as number of flare-free days over 52-week DB period. Age group (3 months- <12 years, ≥ 12 years), duration of the BID treatment in OL period (≤ 4 , >4 weeks), and ISGA score (clear [0], almost clear [1]) at randomization will be included in the model as covariates.

Least square (LS) estimates of mean values and the LS mean differences between crisaborole QD and vehicle QD groups will be derived from the model. The corresponding p-value, standard errors and 95% CI will also be derived from the model.

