6.2.2. Total Number of Flares

The second key secondary endpoint is the number of flares during the 52-week DB period.

- Estimand strategy: Hypothetical ([Section 2.1.2.2](#)).
- Analysis Population: Evaluable-DB.
- Analysis method: Wilcoxon rank sum test stratified by age group, duration of the BID treatment in OL period, and ISGA score at randomization.
- Intercurrent events: intercurrent events include discontinuation of treatment.
- Reporting results: Median for each treatment group and median difference estimated by the Hodges–Lehmann method² along with the 95% CI, p-value from Wilcoxon rank sum test will be reported.

Participants will be ranked in descending order according to the number of flares adjusted for length of time in the DB period, and length of time in flare-free period, ie if participants have same number of observed flares, below conditions will be used as tie-breaker in sequence:

- Participants who prematurely discontinue the study for efficacy reasons (ie, discontinue due to lack of efficacy or AD worsening of AE for treated lesions) will be ranked below others;
- The participant with longer time in the double-blind maintenance period will receive a higher rank;
- The participant with longer time in flare-free period will receive a higher rank.

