6.4. Additional Secondary Endpoints

Analyses of secondary endpoints for OL period will be based on LOCF data.

Analyses of secondary endpoints for DB period will be based on observed data.

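### Number of flare-free days (SAP 6.2.1) is analysed as an observed total but described as a hypothetical estimand, and no analysis addresses early exit

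*SAP*

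**What the plan says.** SAP 6.2.1 defines the endpoint as "total flare-free days during the DB period for each participant regardless censoring or not", and adds that "the censored number of flare-free days in a flare-free period is truncated at censoring for the calculation of total number of flare-free days". The method is ANCOVA. Under SAP 5.2.2.2, age group, duration of BID treatment in the open-label period and ISGA at randomization "will be included in the model as covariates"; nothing else is adjusted for.

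SAP 6.2.1 and Estimand 2 (SAP 2.1.2.1) both call the strategy hypothetical. On intercurrent events, Estimand 2 says "Addressing intercurrent events for the duration of flare-free maintenance at each flare-free period is the same as that for the primary endpoint", and 6.2.1 repeats it. The primary rule in SAP 6.1.1 is that "the duration of flare-free maintenance is the time from randomization to the first intercurrent event and is right censored". The population-level summary in Estimand 2 is the "Difference in least-square means between crisaborole ointment, 2%, QD and vehicle QD for flare-free days over 52 weeks". The 52-week wording is there and in the testing order of SAP 5.1.1, not in 6.2.1 itself.

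For number of flares, SAP 6.2.2 singles out participants who "discontinue due to lack of efficacy or AD worsening of AE for treated lesions". SAP 6.2.1 makes no distinction by reason for leaving.

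**The concern.** The log-rank test for the primary uses a censoring indicator; the ANCOVA does not. Once the durations are summed, their censored status is lost and the total is treated as complete. A participant who leaves without a flare is scored as if every later day were not flare-free. Some exits have nothing to do with efficacy: the protocol requires discontinuation after a broken code (6.3) and withdrawal after a confirmed pregnancy (8.2.5.1).

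A reader who trusts the label would take the LS mean difference and its CI as flare-free days gained over 52 weeks had participants stayed. The analysis estimates flare-free days accrued while on study, which also depends on how long each arm stays. The endpoint is second in the testing sequence, so its estimate is likely to be reported as a confirmed effect size.

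**Working it through.** **1. Is early exit addressed elsewhere?** SAP 6.1.2 concerns the timing of flare onset for the primary only. SAP 5.3 covers open-label data, double-blind descriptive statistics, safety and questionnaire items. The line "Analyses of secondary endpoints for DB period will be based on observed data" stands in SAP 6.4, under additional secondary endpoints. SAP 6.5 gives subgroups. Protocol 9.4.1.2 lists sensitivity analyses for the primary only. None fills the gap.

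**2. What the rule does.** A participant who never flares and leaves on Day 60 scores 60. A completer with three full 12-week flare periods scores 365 − 3 × 84 = 113.

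**3. The plan's own figure.** Protocol 9.2 states about 96% power for 162 events at HR 0.556, two-sided 0.05. Schoenfeld: Φ(½ × √162 × |ln 0.556| − 1.96) = Φ(3.736 − 1.960) = 96.2%. This reproduces. No power is stated for flare-free days.

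**4. Simulation set-up.** From the documents: 125 per arm, 365 days, HR 0.556, 162 first flares. The vehicle flare rate r solves 125 × (2 − e^(−r) − e^(−0.556r)) = 162, giving r = 1.403 per year. The simulated log-rank power is then 95.9%.

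Assumed: 60% flare resolution per 4-week course; withdrawal if a flare is unresolved at 12 weeks; exponential dropout independent of flares; a two-sample t-test in place of the ANCOVA. The documents give no dropout rate, and protocol 7.2 expects withdrawal to be uncommon. Dropout is therefore assumed at 2–15% over 52 weeks, plus unequal cases.

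**5. Hand check.** With 52-week dropout p, mean time on study is 365 × p / (−ln(1 − p)). For p = 5%: 365 × 0.05/0.0513 = 355.8 days. For p = 10%: 365 × 0.10/0.1054 = 346.4 days. The arms differ by 9.4 days on study, most of them flare-free, so a shift a little under 9 days is expected.

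**6. Results without between-participant variation (no frailty).**

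| Dropout, vehicle v crisaborole | True effect | Mean difference, days | Ungated rejection |
|---|---|---|---|
| none | HR 0.556 | 22.9 | 88% |
| 10% v 5% | HR 0.556 | 29.9 (29.9 − 22.9 = +7.0) | – |
| 5% v 10% | HR 0.556 | 13.7 (13.7 − 22.9 = −9.2) | 31% |
| 7% v 5% | none | +3.0 | 5.4% |
| 10% v 5% | none | +7.7 | 12–13% |
| 25% v 15% | none | +16.5 | 28% |

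The last row goes beyond the 2–15% range and is shown only for scale. Allowing for frailty as well, the shift for a 10% v 5% imbalance is about 6 to 9 days. When the primary must first be significant in favour of crisaborole, false claims in the no-effect cases are 0.8–1.3%.

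**7. Power under equal dropout (context only).** At 10% per arm:
- No frailty: 88% falls to 57–59%.
- Gamma frailty variance 0.5, conditional HR 0.475 (log-rank power 97%): 97% falls to about 81%.
- Gamma frailty variance 1, conditional HR 0.42 (log-rank power 96%): 99% falls to about 92%.

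Both frailty cases are calibrated to 162 expected events.

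**The case against.** The strongest reply is that nothing is hidden. The SAP states the truncation openly, and an observed total is a legitimate endpoint; for participants withdrawn with an unresolved flare, adding no further days may be reasonable. Once the endpoint is described as an observed total, the 29.9 and 13.7 days are no longer errors, because 22.9 is not its target. That stands, and it is why the fault lies in the description and the missing second analysis, not in the choice of ANCOVA on a truncated total.

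The size is also model-dependent. The steep no-frailty power loss is not implied by the stated 96%, since frailty settings that give about the same primary power lose much less. Flare resolution matters too. Protocol 4.2 cites a median of 84 days to regain clear or almost clear skin in an earlier study. The wording is ambiguous and may not describe flare treatment here. Read as flare duration, it implies 1 − 0.5^(1/3) = 21% resolution per course, and power then falls only from 88% to 80% at 10% equal dropout. The 113-day completer is an extreme case: at 60% resolution per course, three flares that each resolve only at the third course have probability (0.4 × 0.4 × 0.6)³ = 0.096³, below 0.1%.

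Stronger readings are tempting but unsupported:
- A reader might infer that the plan risks false confirmatory claims. The 12–13% is ungated; behind the primary it is near 1%, and with equal dropout and no effect rejection stays at about 5%.
- A reader might infer that lost power, and the blocked claims for number of flares and pruritus, are the reason to change. The remedy leaves the gating test as it is, so it restores no power.
- A reader might treat the removal of the annualised analysis, recorded in the SAP version history, as a mistake. It is a documented decision, and restoring it is not proposed.

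**Conclusion.** The point holds as a mismatch between description and method. SAP 6.2.1 computes flare-free days observed up to exit. The hypothetical label, the reference to the primary's censoring and the 52-week summary describe something else, and no analysis shows how far the two differ.

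Under the stated assumptions, a 5-point dropout imbalance (10% v 5%) moves the LS mean difference by about 6 to 9 days, in the direction set by which arm loses more participants. That is roughly a third of the base-case effect (7.0/22.9 = 31%; 9.2/22.9 = 40%). With little imbalance it is small: 3.0 days at 7% v 5%. Dropout, flare resolution and between-participant variation are assumptions; the documents give none of them for this design. The primary analysis is not affected. This should be fixed, but it does not threaten the trial's main conclusion.

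**What to change.** 1. Keep the truncated total with ANCOVA as the main analysis. In SAP 2.1.2.1 and 6.2.1, replace the hypothetical label and the reference to the primary's censoring with a statement that flare-free days are those observed up to discontinuation for any reason, and that later days add none. Align the same label in protocol 1.1, 3 and 9.1.1 at the next amendment.

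2. Add one prespecified supplementary analysis aimed at the 52-week value. For exits unrelated to efficacy, multiply impute flare-free days to Day 365 within randomized arm, given flare status and flare history at exit. Count days after efficacy-related withdrawal (the SAP 6.2.2 definition plus a flare unresolved at 12 weeks) as not flare-free. Use the same ANCOVA and combine by Rubin's rules. It is supplementary because it targets a different quantity from the main analysis.

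3. Report time on study and reason for exit by arm beside the LS means. The double-blind disposition summary in SAP 6.6.2 already supplies part of this.

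Cost: text edits in two SAP sections, and one imputation model to specify and program. That model assumes dropout is explained by arm and recorded flare history, so it does not cover dropout driven by unrecorded worsening. Until the protocol is amended, the two documents will carry different labels, and the SAP version history should say why. Protocol 9.4 requires an amendment for major changes to key secondary definitions or analyses. The variable and the ANCOVA do not change, so this does not appear to be one, but the sponsor should record that judgement.
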